This is a repeated measures study that is a pilot randomized controlled trail, four parallel groups, and double-blind design. It is used to examine the effects of Paro intervention on cognition, executive functions, and mental well-being for specific attachment older adults with dementia at before, during and after the intervention. A mixed between-within subjects analysis of variance design will be used to assess the immediate effects of the 6-week Paro intervention on cognitive, executive and three mental well-being related variables for different attachment orientations of older adults living LTC facilities. Outcomes of interest measures will include dopaminergic activities variations by FTT and HRV changes at three time points: before the intervention (T0), middle of intervention (week-3, T1), the end of intervention (week-6, T2), and 1 month after the intervention (T2). Furthermore, the change of oxytocin level will be assessed at baseline and the end of the intervention.

The purpose of this study is to examine the effect of Paro intervention on neurobiologically changes for older adults with dementia in LTC. The research design is shown in Table1.

Table 1 Research design for Paro intervention

Group	Subgroup	T0	Intervention	T1	T2	T3
Security	Experiment	O ₁	X	O ₂	O ₃	O ₄
	Control	O ₁		O ₂	O ₃	O ₄

Experiment group: Paro intervention; Control group; O₁: Baseline; O₂: Week 3; O₃: Week 6; O₄: Week 10

4. Sample size, Sampling, Settings, and Participants Recruitment

There are 120 participants will be recruited into this pilot randomized controlled trial from LTC facilities in southern Taiwan. Older adults will be randomly assigned to four groups: experimental group or control group. The purpose of sampling will be used to allocate 60 participants either to the experimental group or the control group using computer generated sampling. Contact has been made with the Directors of the LTC facilities who have expressed their interest in being involved in the study. Directors will invite older adults who meet the inclusion criteria to participate in this study.

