The inclusion criteria of elderly participants will be: (1) aged 65 years or over; (2) Mild to moderate dementia (3) an ability to communicate in Mandarin or Taiwanese; and (4) has been living in the LTC facility at least 3 months. Older adults who: (1) have severe difficulty in communication; (2) are totally dependent on carers for daily activity; (3) have a diagnosed infectious disease, severe dementia, and severe mental illness such as schizophrenia and delusional disorder, will be excluded from the study.

5. Intervention

Participants in the experimental group will receive a group (6-8 people as a group) , facilitated, and 30-minute weekly session Paro intervention for 6 weeks. The control group will receive care as usual activities, such as painting, drawing, and craft, which are provided by each facility.

6. Paro

Paro (Personal Assistive Robot), was developed by [name] in Japan. It has the appearance of a baby harp seal; the current version (V9) weighs 2.5 kilograms and is approximately the size of a new-born baby. Paro is equipped with an array of tactile sensors that monitor sound, light, temperature and touch via artificial intelligence software. Paro can show human-like emotional reactions when it feels surprised, happy, or angry, and it will cry when it is neglected or not receiving sufficient attention.

In this study, Paro will be used as a Robot-pet companionship intervention with the aim to improve mental health in terms of different attachment orientations. Robot-pet companionship interventions are based on human-animal interactions aimed at providing physiological, psychological, and social benefits (Robinson et al., 2015; Chang et al., 2013; Cohen-Mansfield et al., 2010; Shibata et al., 2004).

Figure 1. The images of Paro

7. Procedure of interaction records

Participants in experimental groups will receive a group, facilitated, 30-minute weekly session of Paro intervention. A trained research assistant (RA) give the Paro to the participants at the start of each session, repeating the same introductory script each time. The RA facilitate the participant interact with the Paro during the intervention, after 30 minutes RA will use the same ending script to end the session and goodbye to participants.

8. Outcome measures

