Data will be analyzed using the Statistical Package for Social Science (SPSS) for Windows software version 26 (IBM Corp.). Data collected will be reviewed for completeness and consistency within a single data form. Approximately 10% of the data entry will be checked for accuracy and consistency (Gad & Taulbee, 1996). Last observation carried forward method will be used to manage missing data at random (Kang, 2013). An intention-to-treat approach (Gupta, 2011) will be used in which all participants will be analyzed according to their enrolment.

Descriptive statistics will be used to analyse demographic data where normality of data distribution for the outcome variables will be examined using probability plots and Kolmogorov-Smirnov tests. Frequency and percentages will be used to summarize categorical variables such as gender and educational level. Mean, standard deviation, and range will be reported to present continuous variables such as age and the score of all scales. Demographic characteristics and baseline data of participants will be compared with different subgroups, using chi-square for categorical variables or t-test (or Mann-Whitney U test) for continuous variables. Relationships between demographic characteristics and outcome measures will be explored using Pearson's correlations. Cronbach's alpha will be used to check the reliability of all instruments.

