To probing the change of the markers, a series of paired sample t-test will be used for each group. To testing the research hypothesis, a mixed designed generalized linear model (GLM) will be employed to test the effects of arms on the differences between the pre and post-test in relation to outcome measures, including oxytocin level, dopamine and HRV changes for different attachment orientations of older adults living LTC facilities. In order to increase precision in estimating the effect of interest, the possible confounding effects of the covariates, such as age, education, etc, will be used to take into account as covariate in the model. The effect size will be calculate to show the magnitude and direction of the effect in the attachment-specific group relative to the control for each outcome variable. In order to identify the optimal duration of clinical application for this intervention, a trend analysis will be conducted. Exploratory additional analysis will be conducted to test the interaction between intervention, and potential biomarker on clinical evaluation. A p value $< .05$ will be taken as the level of statistical significance. The 95% confidence interval around the differences will be calculated.

II. Expectation Outcome

We expect to identify positive effect of Paro intervention on cognitive, executive functions, depression, loneliness, and mental well-being for older adults with dementia.

III. Ethical Considerations

Ethics approval for both phases of the study will be sought from Cheng-Kung University Human Research Ethics Committee and prior to the commencement of the study. Ethics approval for the study will also be sought from the participating LTC facilities in Taiwan prior to the commencement of the study. The researcher will inform the participants about the aims and objectives of the research study and what their participation will involve. Participants will be assured that (a) their participation will be on a voluntary basis and they are under no obligation to participate; and (b) they are free to withdraw from the study at any time without explanation, penalty or compromising their relationship with the LTC. A signed consent form will be sought from each participant. There are no foreseeable risks associated with participation in the intervention for participants.

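### Last observation carried forward is the only missing-data rule; data missing at random do not justify it, and the direction and size of the resulting bias are unknown

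*Combined protocol and SAP*

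**What the plan says.** Study 3, I.8 Data analysis, states: "Last observation carried forward method will be used to manage missing data at random". Study 2, II.8(3) Quantitative data analysis, has the same sentence. Both pair it with an intention-to-treat approach that analyses every participant. No section names another missing-data method or a sensitivity analysis. The one additional analysis in Study 3, I.8 is exploratory and concerns biomarker interaction.

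Study 1 has no data-analysis section. The Study 3 text appears to serve for it: "a mixed designed generalized linear model (GLM) will be employed to test the effects of arms" on pre-to-post differences "in relation to outcome measures, including oxytocin level, dopamine and HRV changes", allowing for "the possible confounding effects of the covariates, such as age, education, etc". The same section adds: "In order to identify the optimal duration of clinical application for this intervention, a trend analysis will be conducted". The design sections of Studies 1 and 3 also say: "A mixed between-within subjects analysis of variance design will be used to assess the immediate effects".

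The finger tapping test (FTT), heart rate variability (HRV) and the Study 3 outcomes are measured at baseline, week 3, week 6 and one month after the intervention. Oxytocin is measured twice (Study 1, II.3 and II.8, Table 2): "the change of oxytocin level will be assessed at baseline and the end of the intervention". Eligible participants have "Mild to moderate dementia" (Study 1, II.4). They may withdraw freely, and the expected-difficulties sections of all three studies foresee that some may be anxious about Paro or withdraw from the intervention.

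**The concern.** The sentence joins two things that do not belong together. MAR says that missingness depends only on observed data. LOCF says that nobody changes after the last visit seen. The first does not imply the second. If the phrase means only that values are missing haphazardly, the difficulty remains, because LOCF can still bias the contrast when arm means move between visits. The trial is built to detect such movement.

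At stake are the arm contrasts for the primary outcomes of Studies 1 and 3, the week-10 follow-up, and the trend analysis meant to identify the optimal duration, which would run on flattened means. The one foreseen reason for withdrawal, unease with Paro, arises in the Paro arm. Unequal dropout is therefore plausible, and that is where the direction of LOCF bias is hardest to predict.

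**Working it through.** The plan has no figure to reproduce: it states no dropout rate, SD, effect size, expected course or power calculation. From the documents come 60 participants per arm and the visit schedule. Everything else below is assumed, in SD units with baseline mean 0.

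**1. Week 6, dropout unrelated to outcome.** A proportion p of those remaining leaves before each visit. Leavers before week 3 carry baseline (0), and those between weeks 3 and 6 carry the week-3 score. With arm means m3 and m6:

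LOCF mean = (1−p)·m3 + (1−p)²·(m6 − m3).

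If half the change has occurred by week 3, this is m6·[1 − f(p)], where f(p) = p + 0.5p(1−p). For p = 0.05, 0.10, 0.15, f = 0.074, 0.145, 0.214. The bias of the contrast (Paro minus control) is mC·f(pC) − mP·f(pP). The true contrast is 0.50 in every row.

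| Arm means at week 6 (Paro, control) | Dropout per visit | LOCF contrast |
|---|---|---|
| 0.5, 0 | equal, 5 / 10 / 15% | 0.463 / 0.428 / 0.393 |
| 0, −0.5 | Paro only, 5 / 10 / 15% | 0.500 / 0.500 / 0.500 |
| −0.3, −0.8 | Paro only, 5 / 10 / 15% | 0.522 / 0.544 / 0.564 |
| −0.3, −0.8 | Paro 5%, control 15% | 0.351 |

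With equal dropout the first row's results hold for any control course of this shape, because the bias is then −0.50·f(p).

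**2. Effect that peaks early.** With flat controls, a contrast of 0.6 at week 3 falling to 0.4 at week 6, and a share d lost after week 3, LOCF gives 0.4(1−d) + 0.6d = 0.42 / 0.44 / 0.46 at d = 10 / 20 / 30%. This is away from zero.

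**3. Dropout that depends on observed scores (MAR).** Take flat controls, Paro means 0, 0.25, 0.50, correlation 0.6 between visits, and control participants with poor week-3 scores leaving more often. A leaver's week-6 score is expected to recover to 0.6 of the week-3 deficit, but LOCF holds the full deficit. By simulation, with 27% of controls and no Paro participants lost, LOCF gives 0.563. With 30% of controls and 10% of Paro participants lost (the latter unrelated to outcome), it gives 0.547. Regression imputation from the first two visits, which is valid under MAR, gives 0.497 and 0.501.

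**4. Oxytocin.** There is no visit between baseline and week 6, so LOCF can carry only baseline. The contrast becomes mP(1−dP) − mC(1−dC). With missingness unrelated to outcome and equal, 0.50 becomes 0.45 at 10% and 0.40 at 20%. With 20% missing in Paro, none in control, and means −0.3 and −0.8: −0.24 + 0.80 = 0.56.

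**5. Week 10.** With flat controls, dropout as in step 1 and Paro means 0.25, 0.50, then 0, LOCF shows 0.25p(1−p) + 0.50p(1−p)² = 0.034 / 0.063 / 0.086 where the true effect is 0.

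**6. Trend.** A true Paro gain of 0.25 from week 3 to week 6 reads 0.25(1−p)² = 0.226 / 0.203 / 0.181.

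**7. No effect.** A shift of 0.3 in both arms, with 15% against 5% dropout per visit, gives a false difference of 0.3 × (0.214 − 0.074) = 0.042.

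**8. Study 2.** The text does not say whether baseline or the week-3 score from Study 3 is carried. For a true mean change of 0.50, half of it by week 3, and 10 / 20% missing at the end unrelated to outcome: 0.50(1−d) = 0.45 / 0.40 if baseline is carried, and 0.50(1−d) + 0.25d = 0.475 / 0.45 if week 3 is carried.

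**The case against.** The best defence is one of scale. The trial calls itself a pilot, losses may be few, and the plan has measures to hold participants: briefings, family involvement, incentives. Withdrawing from sessions also need not mean missing an assessment. At 5% equal dropout per visit the illustrated bias is 0.037 SD, about a fifth of the standard error of an unadjusted difference between two means of 60 (√(2/60) = 0.183 SD). The away-from-zero example in step 1 needs controls to fall 0.8 SD in six weeks, which no section supports. LOCF does keep everyone in the intention-to-treat set, and the alternatives rest on MAR, which cannot be verified.

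Much of this stands, and it limits severity: the documents cannot show the bias to be large. It does not rescue the rule. The stated condition does not support the method, and nothing planned would reveal whether the result depends on it.

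A reader might infer that LOCF is merely conservative and shrinks any Paro effect. The documents do not support that. Shrinkage at week 6 follows if dropout is unrelated to outcome and similar in rate and timing across arms, and benefit builds over visits. A stable control mean alone is not enough, as steps 2 and 3 show. Nor do the documents show that Study 2 changes are set to zero, since week-3 scores exist.

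**Conclusion.** The concern holds. LOCF is the only missing-data method, it is tied to MAR, MAR does not justify it, and no sensitivity analysis is planned. Its extension to oxytocin, FTT and HRV is a reading of Study 3, I.8, which names those outcomes, because Study 1 has no analysis section.

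Direction and size are unknown. In the illustrations a true 0.50 SD week-6 contrast reads from 0.35 to 0.56, depending on each arm's course and on who leaves; these values are not predictions. The firmest consequence needs no assumed size: under this rule every missing week-6 oxytocin value is entered as no change. The plan should be changed, but the trial stays interpretable if few assessments are missed. A claim that LOCF necessarily understates the effect, or that it invalidates the trial, would go beyond the documents.

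**What to change.** Studies 1 and 3: replace LOCF as the primary method with a likelihood-based repeated-measures mixed model on all observed visits (SPSS MIXED: arm, visit, arm-by-visit, unstructured covariance, planned covariates). Keep baseline as an outcome with a common baseline mean in both arms, or use multiple imputation. Participants without a later visit, including those with no week-6 oxytocin sample, then stay in the analysis set as the plan requires; with baseline only as a covariate, they would drop out of the oxytocin analysis. For outcomes far from normal, such as commission errors out of six stop trials (Study 3, I.7(3)), use multiple imputation with a suitable model.

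Study 2: replace LOCF with multiple imputation that uses group climate, satisfaction and the week-3 scores.

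All studies: report missing assessments and reasons by arm, and add one sensitivity analysis for data not missing at random, for example shifting unseen values by a stated amount. Keep LOCF as a sensitivity analysis at most.

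The cost is SAP wording and a record of why each assessment was missed; the software package and visits are unchanged. Standard errors will be somewhat larger, and power can be lower where LOCF is unbiased or biased away from zero. Reliance on MAR remains. If Paro leavers' unseen week-6 values were 0.25 SD worse than the model predicts, the contrast would be overstated by 0.25 × [1 − (1−p)²], about 0.02 / 0.05 / 0.07 SD at 5 / 10 / 15% dropout per visit. The sensitivity analysis is needed for that reason.

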The process and outcome of measurement will be blinded and assessed by another RA at four time points: baseline (T0), Week 3(T1), Week 6 (T2), and 1 month after the end of intervention(T3). The primary outcomes are oxytocin level, FTT results and HRV tests.

Table 2 Measurement time points and measurements

Instrument	Week-0 (T0)	Week-3 (T1)	Week-6 (T2)	Follow-up (T3)
Demographics/disease	√			

information				
Outcome measure				
-oxytocin level	√		√	
-FTT	√	√	√	√
-HRV	√	√	√	√

Note. √, collect data; FTT: finger tapping test HRV: heart rate variability

(1) Demographic data

Participants’ demographics such as age, gender, education level, religion, number of children, and previous pet ownership will be collected. Disease-related information will include the length of stay in the LTC, type of depressive disorder, any other chronic disease, a medication audit including antidepressants and other medications, and Barthel index of Activities of Daily Living.

(2) Oxytocin measurement

Blood samples for the oxytocin assay were collected from the antecubital vein into pre-chilled 5 ml EDTA tubes with 250 KIU of aprotinin, and refrigerated until processing. Plasma was isolated by centrifugation at $1800 \times g$ for 15 minutes at 4°C and stored in aliquots at -70°C. The oxytocin immunoreactivity level was quantified in duplicate using a commercial oxytocin ELISA kit (Enzo Life Sciences, NY, USA, formerly Assays Designs, MI, USA).

(3) Finger tapping test

The FTT consists of tapping with the index finger on a computer mouse as many times as possible within 10 s. The test was repeated three consecutive times and performed randomly across subjects, and the order was kept constant in each subject at each session. The average number of taps was then calculated

(4) HRV measurements

ANS activity. A full 20-minute period of recumbent acclimatization in a quiet room that was maintained at a comfortable temperature (25–27°C) preceded the cardiovascular measurements, which started at 10 AM. Subjects were asked to relax and breathe normally to avoid hyperventilation. Cardiac autonomic function was

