Participants in the experimental group will receive a group (6-8 people as a group), facilitated, and 30-minute weekly session Paro intervention for 6 weeks. The control group will receive care as usual activities, such as painting, drawing, and craft, which are provided by each facility.

6. Procedure of interaction records

Participants in experimental groups will receive a group, facilitated, 30-minute weekly session of Paro intervention. A trained research assistant (RA) will give the Paro to the participants at the start of each session, repeating the same introductory script each time. The RA facilitate the participant interact with the Paro during the intervention, after 30 minutes RA will use the same ending script to end the session and goodbye to participants.

7. Outcome measures

The process and outcome of measurement will be blinded and assessed by another RA at four time points: baseline (T0), Week 3(T1), Week 6 (T2), and 1 month after the end of intervention(T3). The primary outcomes are global cognitive function and executive functions. The Mini-Mental State Examination (MMSE) will be used to assess participants' global cognitive function. The executive functions include two components such as working memory (WM) and response inhibition, which will use computerized tasks to assess the changes of executive functions for order adults before and after intervention. Working memory will be assessed using verbal WM and visuo-spatial WM tasks. Response inhibition will be assessed employing color word stroop

(CWS), stop signal (SS), and go/no-go (GNO) tasks. The secondary outcome measures are loneliness (UCLA version-3), Depression (GDS-SF), and Mental well-being (WEMWBS).

Table 2 Measurement time points and measurements

Instrument	Week-0 (T0)	Week-3 (T1)	Week-6 (T2)	Follow- up (T3)
Demographics/disease information	√			
RAAS-C	√			
Outcome measure				
-MMSE	√	√	√	√
-Executive Functions	√	√	√	√
-Loneliness (UCLA)	√	√	√	√
-Depression(GDS-SF)	√	√	√	√
-Mental well-being (WEMWBS)	√	√	√	√

Note. √, collect data; MMSE; executive function; UCLA, the University of California Los Angeles Loneliness Scale version 3; GDS-SF, Geriatric Depression Scale - Short Form; WEMWBS, Warwick-Edinburgh Mental Well-being Scale.

(1) Demographic data

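### The arm comparison is made on pre-post change, and the outcome's own baseline value is never named as a covariate, which gives up precision that the plan says it wants.

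*Combined protocol and SAP*

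**What the plan says.** Study 1 has no data analysis section. The hypothesis test for its outcomes is set out in Study 3, I.8, where a mixed-design generalized linear model is to "test the effects of arms on the differences between the pre and post-test in relation to outcome measures". The outcomes named there are oxytocin, dopamine and HRV. Study 1, II.8 makes these primary: "The primary outcomes are oxytocin level, FTT results and HRV tests".

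The reason for adjusting is explicit: "In order to increase precision in estimating the effect of interest". The adjustment set is open: "covariates, such as age, education, etc, will be used to take into account as covariate in the model".

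The design sections (Study 1, II.3 and Study 3, I.3) name a different model: "A mixed between-within subjects analysis of variance design will be used to assess the immediate effects of the 6-week Paro intervention". No baseline covariate is mentioned there either.

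Table 2 of each study schedules T0 for every outcome. Oxytocin has one later measurement: "the change of oxytocin level will be assessed at baseline and the end of the intervention".

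Before the hypothesis test, I.8 adds within-arm tests: "To probing the change of the markers, a series of paired sample t-test will be used for each group".

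**The concern.** When precision is the aim, the outcome's own baseline value is the natural first covariate. It is already collected, and it will often predict the follow-up value better than age or education. The plan uses T0 only by subtracting it, or by treating it as one level of the repeated response. Subtraction fixes the coefficient of T0 at 1, whereas ANCOVA estimates it from the data. When the pre-post correlation is well below 1, subtraction overcorrects and adds noise.

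At stake are the width of the confidence intervals and the power of a trial whose 120 participants are not justified by any stated effect size, SD or power. A second consequence is that the two analyses give different estimates whenever the arms differ at baseline. With the covariate list open, the choice between them could be made after the data are seen.

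**Working it through.** **Figures in the plan.** No precision or power figure is available to reproduce. The sample size is 120 (60 per arm), with no derivation.

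**Inputs**
- n = 60 per arm (Study 1 abstract and II.4).
- Significance level .05 (Study 3, I.8). Sidedness is not stated, so two-sided is assumed.
- ρ, the correlation of T0 with follow-up, is not given for oxytocin, FTT, HRV, MMSE, executive functions, loneliness or depression. Assumed values are 0.3, 0.5 and 0.7. The values .79 (Chinese version) and .83 (original) are test-retest reliabilities of WEMWBS (Study 3, I.7(6)), used here only as illustrations of ρ.
- Arm difference of 0.4 SD: assumed.
- Equal SDs at both visits (set to 1), independent participants, no missing data.

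**Step 1: which test is planned.** Oxytocin has two visits only. With two visits, the arm-by-time test of a mixed ANOVA is the same as the two-sample test on change scores. The two models named in the plan therefore coincide for this outcome, and neither has T0 as a covariate.

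**Step 2: variances of the arm contrast**
- Change score: 2(1 − ρ) × (2/n)
- ANCOVA on T0: (1 − ρ²) × (2/n)
- Ratio: (1 − ρ²) / [2(1 − ρ)] = (1 + ρ)/2

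At ρ = 0.5 the change-score SE is √(1.00 × 2/60) = 0.183 and the ANCOVA SE is √(0.75 × 2/60) = 0.158.

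**Step 3: power and equivalent sample size.** Power is from the noncentral t. The last column is 60 divided by the variance ratio.

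| ρ | Variance ratio | Variance saved | Power, change score | Power, ANCOVA | Change-score n per arm to match ANCOVA with 60 |
|---|---|---|---|---|---|
| 0.3 | 0.65 | 35% | 45.1% | 62.5% | 92.3 |
| 0.5 | 0.75 | 25% | 58.4% | 70.9% | 80.0 |
| 0.7 | 0.85 | 15% | 80.1% | 86.1% | 70.6 |
| .79 | 0.895 | 10.5% | 91.8% | 94.3% | 67.0 |
| .83 | 0.915 | 8.5% | 96.1% | 97.4% | 65.6 |

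Confidence intervals shrink by the square root of the ratio: about 19% narrower at ρ = 0.3 (√0.65 = 0.806) and about 5% narrower at .79 (√0.895 = 0.946).

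**Step 4: simulation check.** With 3,000 trials at each of ρ = 0.3, 0.5 and .79, the simulated variance ratios were 0.648, 0.738 and 0.896, against 0.65, 0.75 and 0.895 by formula. Both estimators averaged about 0.40, the true value, so neither is biased under randomisation.

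**Step 5: effect of a baseline difference.** If the arms differ at T0 by d₀, the change-score and ANCOVA estimates differ by (1 − ρ) × d₀. For an assumed d₀ of 0.2 SD this is 0.14, 0.10, 0.06, 0.04 and 0.03 SD at the five ρ values. The standard error of a chance baseline difference with 60 per arm is √(2/60) = 0.183 SD, so 0.2 SD is about 1.1 standard errors and would not be unusual.

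**The case against.** The strongest reply is that the plan contains no error here. A change-score comparison is valid under randomisation. The covariate list is open, so T0 is not excluded. In a mixed model T0 is already present as a level of the response, so one would not expect to find it listed as a covariate as well. All of this stands, and it is why the point concerns precision only. It does not remove the point: T0 as a response level gives the change-score test for oxytocin, and an open list does not commit anyone to adjusting for T0.

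The size of the gain is also undocumented for every primary outcome of Studies 1 and 3. At the two WEMWBS values, power rises by only 2.5 and 1.3 percentage points (94.3 − 91.8 and 97.4 − 96.1), and those reliabilities are not correlations from T0 to week 6 in this population. That stands too. A small gain is possible, but a material loss at lower correlations cannot be ruled out.

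The power figures are illustrative. Paro is given in groups of 6–8 (Study 1, II.5), so absolute power may be lower, and carrying the last observation forward (Study 3, I.8) can itself alter the pre-post correlation.

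Finally, Study 1, V.2 and Study 3, IV.2 recruit the two arms from separate levels. If that produces systematic baseline differences, the efficiency argument no longer settles which estimate to prefer. This is a fair limit, and the reason to keep both analyses with their roles fixed in advance.

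**Conclusion.** The point holds as a matter of efficiency and specification, not validity. The planned test uses the pre-post difference and nowhere commits to adjusting for the outcome's own T0 value, although the plan gives precision as its reason for using covariates. Under equal SDs, a single pre-post contrast and independent participants, the variance given up is 15% to 35% for assumed correlations of 0.7 down to 0.3, and about 10% at the only values in the document, which belong to a secondary scale. The true figure for oxytocin, FTT, HRV, MMSE and executive functions is unknown. Because the remedy uses data already scheduled, the change should be made. The lack of a descriptive label on the per-arm paired t-tests is a minor wording matter, since I.8 already keeps them apart from the hypothesis test.

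**What to change.** Revise Study 3, I.8, and align the two design sections with it:

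1. State that each Study 1 and Study 3 outcome is compared between arms on the follow-up score, with that outcome's T0 value as a covariate alongside age and education, and with a 95% confidence interval. List the Study 3 outcomes by name, since the sentence now names only those of Study 1.
2. For oxytocin, use the week 6 value in an ANCOVA. For the other outcomes, use a baseline-adjusted repeated-measures model over weeks 3 and 6 and the one-month follow-up.
3. Replace the open-ended list with a complete covariate list, fixed before analysis.
4. Keep the change-score estimate as a sensitivity analysis, because the arms are to be recruited from separate levels and the two estimates can disagree if the arms differ systematically at baseline.
5. Label the per-arm paired changes as descriptive.

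The cost is wording only, with no new data or visits. It does re-specify the main model, so it should be settled before analysis. For the two-visit outcome the change is slight: a change-score model with T0 added as a covariate gives the same arm estimate as ANCOVA on the follow-up score.
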